#### To the Study Sponsors:

### NIH/NIAAA

SAEs considered at least possibly related to study participation will be documented and reported to NIAAA within 48 hours with copies included in the participant's file.

### Tilray

If an SAE occurs after the subject signs informed consent through the end of study participation, the PI or a qualified designee will complete the Tilray SAE Form and send it via email to contacts designated by Tilray within

24 hours of the site becoming aware of the SAE. The form must be completed and submitted to Tilray any time a serious medical event has occurred in a participant during the clinical trial, whether or not it is considered related to the study treatment, including active comparators and placebo.

Ensure that an investigator has reviewed and signed the SAE form prior to submission.

Every exposure during pregnancy (participant) should be reported on an SAE worksheet as a case of special interest from the time of study enrolment to the end of study participation.

The following timelines describe when Tilray, as the manufacturer of IP, has to report ADRs to Health Canada:

- Fatal or life-threatening unexpected ADRs require notification of regulatory agencies as soon as possible but no later than 7 calendar days after first knowledge by Tilray that a case qualifies, followed by as complete a report as possible within 8 additional calendar days. The report will include an assessment of the importance and implication of the findings, including relevant previous experience with the same or similar medicinal products.
- All other serious, unexpected ADRs must be filed as soon as possible but no later than 15 calendar days after first knowledge by Tilray that the case meets minimum criteria for expedited reporting.

## 15.3 UP Reporting

Incidents or events that meet the OHRP criteria for UPs involving risks to subjects or others require notification of the local IRB. The phrase "unanticipated problems involving risks to subjects or others" is found but not defined in the HHS regulations at 45 CFR part 46. Any incident, experience, or outcome that meets all of the following criteria is considered to be Reportable New Information (RNI) and is required to be promptly reported to the local IRB:

- unexpected (in terms of nature, severity, or frequency) given (a) the research procedures that are described in the protocol-related documents, such as the IRB-approved research protocol and informed consent document; and (b) the characteristics of the subject population being studied;
- related or possibly related to participation in the research (in this guidance document, possibly related means that, in the opinion of the PI, the incident, experience, or outcome was more likely than not caused by procedures involved in the research); and
- suggests that the research places subjects or others at a greater risk of harm (including physical, psychological, economic, or social harm) than was previously known or recognized.

OHRP recognizes that it may be difficult to determine whether a particular incident, experience, or outcome is unexpected and whether it is related or possibly related to participation in the research. OHRP notes that an incident, experience, or outcome that meets the three criteria above generally will warrant consideration of substantive changes in the research protocol or informed consent process/document or other corrective actions in order to protect the safety, welfare, or rights of subjects or others.

The RNI report will include the following information:

- Protocol identifying information: protocol title and number, PI's name, and the IRB project number;
- A detailed description of the event, incident, experience, or outcome;
- An explanation of the basis for determining that the event, incident, experience, or outcome represents an UP;
- A description of any changes to the protocol or other corrective actions that have been taken or are proposed in response to the UP.

UPs must be reported using the following timeline:

- UPs that are SAEs will be reported to the IRB and to the study sponsor according to SAE reporting procedures described above (within 48 hours of the investigator becoming aware of the event).
- UPs that meet the requirements for RNI will be reported to the IRB as soon as possible and within 5 working days of the site becoming aware of the event.

• All other UPs not related to study activities or that do not result in harm to participants will be reported to the IRB annually in the application for the study's continuation renewal.

## 15.4 Pregnancy Reporting

Pregnancy information on clinical study subjects is collected by the investigator. If a subject should become pregnant during the course of the study, the investigator or qualified designee will contact the IRB within 5 working days of the PI or qualified designee first becoming aware of the pregnancy.

Tilray Pregnancy Reporting Requirements: Every exposure during pregnancy (participant) should be reported on a Tilray SAE worksheet within 24 hours of the site becoming aware of the pregnancy as a case of special interest from the time of study enrollment to the end of study participation. If an SAE occurs in conjunction with the pregnancy, then the Tilray reporting timeframe for an SAE (24 hours) must be met. In the event of a pregnancy, administration of study medication will be discontinued, but all other follow-up data, including safety data, will be collected.

Pregnancies resulting in congenital abnormalities or birth defects in offspring meet the requirements for an SAE and will be collected, documented, and reported according to the procedures outlined above for SAEs.

# 16 Reporting of Investigational Medicinal Product Quality Complaints

## 16.1 Defect or Possible Defect in the IP

Any defect or possible defect in the investigational medicinal product (defined as a pharmaceutical form of an active substance or placebo being tested or used as a reference in a clinical trial) must be reported by the PI or qualified designee to Tilray within 48 hours of first becoming aware of the possible defect. This report to Tilray may be made by telephone or by email. The product and packaging components in question, if available, must be stored in a secure area under specific storage conditions until it is determined whether the product is required to be returned for investigation of the defect. If the product complaint is associated with an SAE, the SAE must be reported separately in accordance with the protocol, and the SAE report should mention the product quality complaint.

## 16.2 Temperature Deviations

In the event that the temperature at which the IP is stored is less than 2°C or greater than 8°C, the CRC and PI will be notified immediately and a temperature deviation form will be completed and sent via email to contacts designated by Tilray as soon as possible. Tilray will provide further guidance on how to proceed on a case-by-case basis.

# 17 Study Halting Rules

When three severe AEs are determined to be "probably related" to the study agent, the DSMB will be informed and asked to convene in order to determine whether action should be taken. The Principal Investigator will inform the DSMB members within 24 hours of this occurrence and will provide the DSMB with AE listing reports. The DSMB will convene an ad hoc meeting by teleconference or in writing as soon as possible. The DSMB will provide recommendations for proceeding with the study to the Principal Investigator. The Principal Investigator will inform the FDA of the DSMB's decision and the disposition of the study. If the DSMB finds it is likely that CBD is contributing to negative outcomes, they will consider solutions including protocol changes or potentially stopping the study.

# 18 Safety Oversight

The research team (project manager, coordinators, and research assistants) will submit any adverse events to the PI and the Data and Safety Monitoring Board (DSMB). The PI and the DSMB members are responsible for reviewing all AEs and serious adverse events (SAEs) reported. All SAEs will be reviewed at the time they are reported in the electronic data capture system. Where further information is needed, the DSMB will discuss the

The PI will generate and present reports for DSMB meetings. The DSMB will receive listings of AEs and summary reports of all SAEs at a frequency requested by the DSMB, but at least annually. Furthermore, the DSMB will be informed of expedited reports of SAEs.

### Data and Safety Monitoring Board (DSMB)

A Data and Safety Monitoring Board (DSMB) will be established, comprising three to five individuals appointed by the PI. The committee will include [name], [name] [name] and [name]. This committee will meet (in person or by teleconference) prior to enrollment of the first participant, and at least annually thereafter, including meetings following completion of treatment of the first 5 completers, after completion of treatment of the first 20 completers, and upon completion of enrollment for the trial. Prior to each meeting, the PI will prepare a report to the Board including review of:

- Protocol and ICF changes
- Protocol violations and deviations
- Documentation of informed consent
- Enrollment and retention
- Investigator or key personnel changes
- Aggregate analysis of adverse events/serious adverse events
- Protection of confidentiality

Following each meeting, the board will provide the PI with a report including a recommendation to continue the study unchanged, continue with modifications of the protocol and/or the consent form to protect participant safety, or terminate the study. Reports will be submitted to the IRB on at least an annual basis.

# **19 Clinical Monitoring**

Site staff will be required to audit source documentation, including informed consent forms and HIPAA forms, regulatory documents and case report forms on a biannual basis. Site staff will be responsible for local quality assurance and will verify that study procedures are properly followed and that site staff are trained and able to conduct the protocol appropriately. If the site staff's review of study documentation indicates that additional training of study personnel is needed, this will be arranged as per the PI. Study team members will review each other's data for completeness, accuracy, and fidelity to the protocol.

# 20 Statistical Considerations

## 20.1 Statistical and Analytical Plans (SAP)

A formal SAP will be developed prior to database lock and unblinding.

## 20.2 Statistical Hypotheses

Hypothesis 1a Safety and tolerability: CBD will be safe and well tolerated and will not lead to increased plasma THC. No clinically significant cognitive or motoric impairments, CBD-related serious adverse events, persisting adverse effects or treatment associated increases in plasma THC will be observed.

Hypothesis 1b: Alcohol use. Relative to the placebo-treated group, CBD-treated participants will have fewer drinks per day during the 6 weeks of treatment with CBD vs placebo.

Hypothesis 2: PTSD symptoms. Relative to the placebo-treated group, CBD-treated participants will lower PTSD symptoms during the 6 weeks of treatment with CBD vsplacebo.

Hypothesis 3a: Mechanism, traumatic stress-induced craving: Relative to placebo, CBD will be associated with a greater reduction between baseline and end of treatment in trauma induced alcohol craving, negative emotion, and psychophysiological arousal in response to the task.

Hypothesis 3b: Mechanism, AUD and PTSD related measures and cognition: Relative to placebo, CBD will improve self-report measures of craving, anxiety, mood, self-efficacy and cognitive performance.

Hypothesis 3c: Mechanism, anandamide: Relative to placebo, CBD will be associated with a greater increase

Hypothesis 4: CBD plasma levels. Within-group plasma CBD levels will stabilize within one week, i.e. 45 minutes post-CBD dosing levels obtained after 1 week of treatment will not differ from those obtained after 4 weeks of treatment at each dose.

Exploratory Hypothesis 1: Relationship between effects on PTSD symptoms and alcohol use. The onset of reduction in PTSD symptoms will precede the onset of reduction in alcohol use.

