The proposed study is a double-blind, randomized proof-of-concept study designed to assess feasibility and contrast effects of CBD treatment to those of placebo on safety, drinking-related outcomes and PTSD/subthreshold PTSD related outcomes in patients with AUD+PTSD/subthreshold PTSD. We will evaluate the safety of an extended daily CBD treatment regimen in an AUD+PTSD/subthreshold PTSD population and measure resulting CBD, THC, and anandamide levels. We will also generate preliminary data on the impact of CBD on alcohol use, PTSD symptoms, a human laboratory traumatic stress induced craving task, neuropsychological and neurophysiological domains implicated in AUD and PTSD/subthreshold PTSD, and cognitive ability. Cannabidiol levels will be obtained from CBD-treated participants to estimate the plasma levels corresponding with putative therapeutic effects and to determine whether dose accumulation occurs. THC levels will be obtained from CBD-treated participants to determine whether CBD metabolites are converted into THC, as has been suggested in the literature [77]. Anandamide levels will be obtained from all participants to test whether CBD elevates plasma anandamide, and to provide preliminary data for relating anandamide levels to putative therapeutic effects. Following screening and baseline assessments, 48 participants will be randomized in a 5:3 ratio to receive either 600mg CBD/day (PO) or placebo respectively for 6 weeks (N=30 participants on CBD and N=18 participants on placebo). Safety measures (adverse events, cognitive and motoric function), drinking related outcomes and PTSD symptoms will be assessed weekly throughout the study. Human laboratory tasks, neuropsychological domains implicated in AUD and PTSD/subthreshold PTSD and cognition will be assessed at baseline and at the end of treatment. Measurement of circulating levels of Delta-9 THC, 11-Hydroxy Delta-9 THC and Delta-9 Carboxy THC will be obtained from CBD-treated participants only at baseline, 45 minutes, 1 day, 1 week, 2 weeks, 4 weeks, 6 weeks, and 7 weeks after treatment with the first dose of CBD vs. placebo. Anandamide levels will be obtained from both CBD- and placebo-treated participants at the aforementioned timepoints.

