## 3.2 Secondary Objectives

Secondary objectives of this study are as follows.

- To assess the effect of CBD upon plasma CBD and THC levels when administered to patients with AUD+PTSD/subthreshold PTSD. We predict that within-group plasma CBD levels will stabilize within one week, i.e. 45 minutes post-CBD dosing levels obtained after 1 week of treatment will not differ from those obtained after 4 weeks of treatment.
- 2) To contrast the effects of CBD to those of placebo on psychological and cognitive domains relevant to AUD and PTSD/subthreshold PTSD. Relative to placebo, we predict that CBD will improve self-report measures of craving, anxiety, mood, and self-efficacy, and improve cognitive function. We will also specifically target the domain of traumatic stress induced craving using a human laboratory task. We predict that relative to placebo, CBD will lead to a greater attenuation in subjective traumatic stress and alcohol cue-induced craving and accompanying physiological stress response.
- 3) To assess the effect of CBD on plasma anandamide levels. We will contrast levels of plasma anandamide between samples taken at baseline and after CBD treatment, and between samples taken at predicted preand 45 minutes post-dosing CBD levels. We predict that relative to placebo, CBD will lead to an increase in plasma anandamide between these time points.
- 4) To assess the temporal relationship between the onset in reduction of PTSD symptoms and the onset in reduction of AUD symptoms. We predict that a reduction in PTSD symptoms will precede a reduction in

Exploratory Aim 1: To examine voicemarkers as a function of a patient's AUD and PTSD status and to develop assessment models that use lexical and prosodic features to classify a patient's AUD and PTSD status.

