# 7.2.2.2 Visit 4 (1 day after Baseline/Enrollment Visit +5 days)

#### 1 day (T2)

- Perform alcohol breathalyzer to obtain BAC
- Collect blood and plasma for CBD, Delta-9 THC, 11-Hydroxy Delta-9 THC, Delta-9 Carboxy THC and Anandamide levels (45 minutes post-CBD levels).
- Collect urine for urine drug analysis
- Record adverse events as reported by participant or observed by investigator
- Record vital signs, concurrent medications, and results of evaluations of safety, cognitive function and psychomotor effects
- Record participant's adherence to treatment program
- Evaluate and record alcohol use

## 7.2.2.3 Visit 5

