### 20.3 Description of Statistical Methods

### 20.3.1 General Approach

We recognize that the relatively small sample sizes proposed in the RCT are not likely to produce statistical significance, unless the effect sizes are remarkably high. We will carry out a full Mixed Model Repeated Measures (MMRM) statistical analysis in case CBD does perform so well. However, the main focus of the statistical analysis of the results of the trial will be to characterize the effect sizes and response rates across the various measurement domains and the profiles of individuals who are treatment successes. The intent to treat (ITT) population will contain all randomized patients who receive at least one dose of double-blind study medication and from whom at least one post-baseline (B1) efficacy measurement is obtained while on study medication. The efficacy analysis will be based on the ITT population. Two-sided hypothesis testing will be utilized. Tests with p-values less than or equal to 0.05 will be considered statistically significant, while those less than equal to 0.10 will be considered suggestive. Since this trial is the first use of this treatment for this diagnostic indication, no adjustments of p-values for multiple comparisons will be made. Thus, all control of type 1 error is contrast-wise. All confidence intervals will be two-sided with 95% confidence. Mean treatment effect, standard errors, and 95% confidence intervals will be derived from fully adjusted models on outcomes averaged across the treatment period. Cohen's d and p-values will be calculated from fully adjusted models with appropriately transformed outcome variables. For dichotomous drinking outcomes, prevalence rates will be calculated. Odds ratios (ORs) and p-values will be derived from logistic regression models including treatment group.

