#### #S17-00949

scores between Post and Pre. This difference measure of alcohol craving will be calculated at Baseline, and at week 6 of the clinical trial (T8). The outcome analysis will be conducted with an MMRM model that includes fixed effects for treatment C, (CBD vs. placebo) and clinical trial time T, a random effect for subjects, and a treatment by clinical trial time interaction (C\*T). The model will provide least-square mean estimates of difference scores at each session for each treatment. Between treatment outcome contrasts will be performed at Baseline, as a measure of the equivalence of the groups, and at T6 and for the difference between T6 and Baseline. For parameter estimation, the form of the covariance matrix will follow the procedures described for the analysis of Aim 1. Secondary outcome measures will be Negative Emotion, and Psychophysiological arousal. These outcomes will be analyzed in a similar manner to the primary outcome, alcohol craving.

For Hypothesis 3b: Mechanism, AUD and PTSD related measures and cognition (craving, self-efficacy, anxiety, cognitive measures) will be analyzed in the same way as the primary outcome for alcohol use. The primary contrast is change from baseline (B1) at week 6 (T8).

For Hypothesis 3c: Mechanism, anandamide, within- and between-group comparisons of plasma anandamide levels will be assessed following 45 minutes (T1), 1 day (T2), 1 week (T3), 2 weeks (T4), 4 weeks (T6), 6 weeks (T8) of treatment with CBD vs. placebo, and one week (T9) after the completion of treatment. Effects of dose will be assessed and the interaction between group and time- point will be evaluated.

For Hypothesis 4, plasma CBD and THC levels will be analyzed in the same manner as anandamide in Hypothesis 3c.

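### Hypothesis 4 predicts that CBD levels do not change between week 1 and week 4, but the plan offers only a difference test and no margin by which stability could be concluded

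*Combined protocol and SAP*

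**What the plan says.** The secondary objectives (Section 3.2) state: "We predict that within-group plasma CBD levels will stabilize within one week". They define this as 45-minute levels at week 1 that "will not differ from those obtained after 4 weeks of treatment". Hypothesis 4 in Section 20.2 repeats the prediction: 45-minute "post-CBD dosing levels obtained after 1 week of treatment will not differ from those obtained after 4 weeks of treatment at each dose". Section 2.3 gives one purpose of the CBD measurements as "to determine whether dose accumulation occurs".

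For the analysis, Section 20.3.3 says that "plasma CBD and THC levels will be analyzed in the same manner as anandamide in Hypothesis 3c". The anandamide text plans comparisons within and between groups at each sampling visit, and a group-by-time interaction. Section 20.3.1 supplies the criterion: tests are two-sided, "Tests with p-values less than or equal to 0.05 will be considered statistically significant", and confidence intervals are 95%. Section 20.3.4 adds means and standard deviations of CBD by visit.

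No section gives a margin, an equivalence test, a rule linking an interval to stability, or a power figure for this comparison. Section 7.2 restricts CBD levels to the CBD arm (30 participants), and Section 5.7.2 says that withdrawals are not replaced. Section 20.1 leaves the formal SAP to be written before database lock and unblinding.

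**The concern.** The prediction is one of similarity, while the method is a test for difference. Failing to detect a difference does not show that levels are alike. It may only show that the data are imprecise. For most hypotheses in this trial imprecision works against the sponsor's prediction, but here it works in its favour. Section 20.3.1 itself expects that samples of this size will seldom reach significance.

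Two things rest on the answer. The trial sets itself the question of accumulation. Sections 4.2.2 and 7.1.8 also expect steady state to have been reached when the stress task is run at T6.

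**Working it through.** **The plan's own figure.** There is none for this comparison. The effect size of 0.939 in Section 20.4 concerns a two-sample t test between arms and cannot be carried over to paired CBD levels.

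**Inputs from the documents.** At most 30 pairs (CBD arm, no replacement); two-sided α = 0.05.

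**Inputs assumed.** Within-person CV of 20% to 80%, because the documents give none; log-normal levels; true week 4/week 1 ratios of 1.3 and 1.5.

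**Formulas.** On the log scale, the SD of the week 4 minus week 1 difference is √(2·ln(1+CV²)). Its standard error is that SD divided by √n. The noncentrality is ln(ratio)/SE. The chance of a non-significant result is P(|T| < t₀.₉₇₅), with T noncentral t on n−1 degrees of freedom.

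**Worked case, CV 40%, n = 30, ratio 1.3.**
- SD = √(2·ln 1.16) = 0.545
- SE = 0.545/√30 = 0.0995
- Noncentrality = 0.2624/0.0995 = 2.64
- Critical t on 29 df = 2.045
- Chance of non-significance = 28%

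**Chance of a non-significant result, 30 pairs:**

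| CV | True 30% rise | True 50% rise |
|---|---|---|
| 20% | 0.1% | about 0% |
| 30% | 8% | 0.1% |
| 40% | 28% | 2% |
| 60% | 58% | 22% |
| 80% | 71% | 42% |

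**Fewer pairs.** For a 30% rise at CV 40%, 60% and 80%, the chance is 36%, 64% and 76% with 25 pairs, and 47%, 70% and 80% with 20 pairs.

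**Larger rise.** With 30 pairs, a doubling would be missed 0.3% of the time at CV 60%, 4% at CV 80% and 12% at CV 100%.

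**What a margin would do.** The rule is that the 90% interval for the ratio must lie within the margin (two one-sided 5% tests, 30 pairs, by simulation). Both margins below are illustrations; the documents give none.
- 0.80–1.25, true ratio 1: stability is concluded 99%, 78%, 42%, 14% and 3% of the time at CV 20%, 30%, 40%, 50% and 60%. At a true ratio of 1.25 it is wrongly concluded about 5% of the time at most.
- 0.67–1.50, true ratio 1: 98%, 74% and 41% at CV 40%, 60% and 80%. Under a true 30% rise it still concludes stability 86%, 58% and 41% of the time at CV 20%, 30% and 40%, because a 30% rise lies inside that margin.

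**Sampling windows.** T2 is "1 day after Baseline/Enrollment Visit +5 days", so day 1 to 6. T3 is one week ± 5 days, so day 2 to 12. The two overlap on days 2 to 6, so a T3 sample may not represent one week of dosing.

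**The case against.** A reader might infer that the trial will declare CBD levels stable whenever p exceeds 0.05, and that this would often hide real accumulation. The documents do not support either statement in that form. No section says that non-significance means stability; Hypothesis 4 is worded as a prediction. Section 20.3.1 puts the main emphasis on effect sizes and plans confidence intervals, Section 20.3.4 describes levels by visit, and the formal SAP is still to come. How often a rise would be missed depends on a CV that the documents do not give. At CV 20% or 30% a 30% rise is missed at most 8% of the time, and a doubling is rarely missed even at high variability.

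Three further points stand:
- The pre-dose samples are not ignored. The Protocol Summary lists them at T3, T4, T6 and T8 among the planned comparisons; only the sentence defining stability leaves them out.
- The comparisons cover more visits than the two modelled here, so a continuing rise could also show at weeks 2 and 6.
- An early T3 sample, taken before levels plateau, would tend to create a week 1 to week 4 difference, not conceal one. The window problem is therefore about what T3 measures and does not add to the risk of a false finding of stability.

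What the objection does not remove is the gap itself. The difference test is the only criterion supplied for the prediction, and an interval or a table of means without a stated bound cannot settle it.

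**Conclusion.** The point holds as a mismatch between hypothesis and method. A prediction of no difference is paired with a two-sided difference test, with no margin, on at most 30 pairs. That is so at every CV. Its practical size is conditional: negligible for a 30% rise at CV 20%, about one chance in four at CV 40% (28%), and more likely than not from CV 60% (58%), with higher figures if pairs are lost. These figures rest on assumed CVs, log-normal levels and a paired comparison of two visits.

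This is a secondary pharmacokinetic prediction in a pilot, and no stopping rule in the documents is tied to it. It is a cheap improvement.

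**What to change.** In the SAP, for CBD-arm participants:
- Analyse log-transformed levels and report the T6/T3 geometric mean ratio with a 90% confidence interval, separately for the 45-minute and the pre-dose samples.
- Use the actual day of sampling, because the T2 and T3 windows overlap.
- State and justify a margin before unblinding: the largest rise the sponsor would regard as unimportant. The range 0.67–1.50 is only an illustration and would tolerate a 30% rise.
- Conclude stability only if the interval lies within the margin. Otherwise report the ratio and interval as stability not established. Say explicitly that p > 0.05 will not be read as stability.

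The cost is wording only; both sample types are already scheduled. The downside is that the answer may be not established if variability is high. With 30 pairs, a 0.80–1.25 margin has about 42% power at CV 40%, and the SAP should state that limit.
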